- Self-management score 18 (of a possible 20) or below on the Diabetes Self-Management Questionnaire (DSMQ)

Exclusion Criteria are:

- Dementia (diagnosis or CDR \geq 1) or prescribed AD medications
- Major medical, psychiatric, or neurological conditions that affect cognitive performance; MMSE <25

- Severe impairment of vision, hearing or fine motor control necessary for computer operation

Eligibility criteria are assessed after potential participants are enrolled by providing signed informed consent at baseline (Visit 1). Following baseline assessment and determination of eligibility, participants are randomized to the CCT intervention, Cognifit, or the active control task. The CCT intervention has games that adapt to the changing performance level of the participant; the active control alternative, has the same games except that they do not adapt to performance, remaining instead at baseline levels. At Visit 2 are introduced to their respective program and are asked perform it 3 days per week (every other day), for 20 minutes, for 24 total sessions. Four months after the intervention, subjects receive a 1-week booster training. Visits 3, 5, and 6 are outcome assessments at the immediate finish of the intervention, six months post-intervention, and 12 months post-intervention, respectively (Figure 1).

[figure not shown]

Figure 1. Timeline of visits from the initial assessments (Month 1; M1) to the final assessments 14 months later.

One of the challenges of internet-based behavior change programs is keeping participants interested and engaged for a sufficient duration, which can be important to ensure a therapeutic benefit. To strengthen participation rates and adherence, staff members call participants once a week, to ask if they are performing the program and if they have any technical difficulties. Nevertheless, we acknowledge that despite these efforts, attrition of subjects occur. Drop out are recorded and Cognifit maintains records, available to this study, of the date and time of each session for each participant in each group.

3. Primary Analysis Objective

The primary outcome measure of this randomized clinical trial (RCT) is the change in DSMQ from baseline (Visit 1) to 6 months after the intervention (Visit 5). The primary analysis is the intent-to-treat (ITT; all enrolled and eligible participants who are randomized) comparison of the two arms of the trial.

4. Analysis Sets/Populations/Subgroups

Intent-to-treat (ITT)

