Descriptive statistics for all relevant variables will be calculated and examined at baseline and subsequent visits. The memory and executive functions/attention scores will be the derived domain scores after taking account of missing data. Substantially non-normal distributions will be transformed to reduce the influence of extreme values. All continuous variables will be summarized using the following descriptive statistics: *n* (non-missing sample size), mean, standard deviation, median, quartiles, maximum and minimum. The frequency and percentages (based on the non-missing sample size) of observed levels will be reported for all categorical measures. All summary tables will be structured by group.

Statistical Procedures

The analytic procedure to address the efficacy of CCT will use linear mixed models (LMM) procedures to evaluate change from baseline (Visit 1) to six months post-treatment (Visit 5). Models will include time (coefficient estimate β_1), intervention group (coefficient estimate β_2), and the intervention group by time interaction (coefficient estimate β_3) which indicates whether the change in outcome over time differs between the intervention groups, all as fixed factors, and subjects as a random factor.

The model for the primary outcome (DSMQ) or any of the seven secondary outcome variables (*Y*) for subject *i* and visit *j* at time t_{ij} is:

$$Y(t_{ij}) = b_0 + b_1 t_{ij} + b_2 \text{Group}_i + b_3 t_{ij}\text{Group}_i + u_i + e_{ij}$$

where b_s estimate the fixed effects of group and time, *u* is the subject random effect, and *e* is the residual error. If the result of randomization is that there is a significant ($P < 0.05$) discrepancy between the two arms of the RCT on any of the primary covariates,

that covariate will be included in the model. Since this estimate will be valid for the ITT population under the MAR assumption, it will not be biased in favor of groups with greater dropout.

Although hypothesized demonstration of benefit of CCT beyond that of the active control is directional, tests of significance will be a two-sided at the 0.05 level, to test for the possibility that CCT is substantially inferior to the active control.

Similar procedures will be employed to compare the treatment arms on change from baseline to other visits for the all outcomes.

Analysis for medication adherence

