In contrast to all other outcome measures, which are assessed at each visit and primarily used to compare Visit 1 to Visit 5, medication adherence is measured only twice the year before Visit 1 and the year after Visit 3. The LMM and model are exactly the same except the two times are Visit 1 and a year after Visit 3 for the particular participant.

Measures to Adjust for Multiplicity, Confounders, Heterogeneity, Etc.

As this study may be considered preliminary to a potential subsequent large-scale multi-site study of CCT throughout the VA, each secondary outcome will be tested at the 0.05 level.

Secondary analyses controlling for primary covariates are described in #4, ITT analysis. With regard to secondary covariates, such as ethnicity, health literacy, or computer experience, if any are unbalanced or correlate with an outcome at $p < 0.05$, it will be used as a covariate in a secondary analysis, to reduce within-group variation.

Subject Disposition & CONSORT Diagram

We will report the number of subjects, in each group and in the aggregate, that reached:

- Screen
- Randomization
- Baseline
- At least one follow-up
- Each follow-up

We will also summarize attrition rate and reasons for discontinuation if we have them.

8. Sensitivity Analysis

Not applicable.

9. Interim Analysis

Not applicable.

10. Rationale for Any Deviation from Pre-Specified Analysis Plan

Not applicable

11. QC Plans

All variables are examined for errors.

12. Programming Plan

Data are maintained in Excel files. Statistical analysis will proceed using SAS 9.4, Stata v13.1 and SPSS.

13. Appendices

Not applicable.

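### With dropout, the random-intercept-only primary model does not support the SAP's statement that its estimate is valid under MAR; the effect at the DSMQ entry cut of 18 is small, and an unstructured covariance removes it.

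*SAP*

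**What the plan says.** SAP section 7 (Statistical Procedures) writes the primary model out in full: intercept, time, group, group by time, a subject effect u_i and a residual e_ij. The first three model terms are "all as fixed factors, and subjects as a random factor". It names no random slope, residual covariance structure or robust standard error. The model's purpose is "to evaluate change from baseline (Visit 1) to six months post-treatment (Visit 5"), and b3, the group-by-time coefficient, carries the comparison.

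The same section justifies the handling of dropout: "Since this estimate will be valid for the ITT population under the MAR assumption", and concludes that the estimate is not biased toward groups that lose more participants. Section 8 lists sensitivity analysis as not applicable, so no other analysis tests that statement.

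Section 2 restricts entry on the primary outcome itself: "Self-management score 18 (of a possible 20) or below on the Diabetes Self-Management Questionnaire (DSMQ").

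Which visits enter the fit is not stated outright. Other visits are handled separately: "Similar procedures will be employed to compare the treatment arms on change from baseline to other visits for the all outcomes". The medication paragraph says "The LMM and model are exactly the same except the two times are Visit 1 and a year after Visit 3", which implies two times in the main model as well. Yet the outcomes are ones "which are assessed at each visit and primarily used to compare Visit 1 to Visit 5", and the equation carries a general visit index j.

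**The concern.** A random intercept with independent residuals is compound symmetry: one variance and one correlation for all visits. A likelihood analysis of incomplete data uses the fitted covariance to infer what the missing Visit 5 values would have been, given Visit 1. MAR therefore protects the estimate only if that covariance is adequately specified.

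The trial's own entry rule makes the equal-variance assumption doubtful for DSMQ. Selecting on Visit 1 narrows the spread at Visit 1 far more than at Visit 5. If dropout depends on the baseline score and differs between arms, b3 is then biased, possibly in the direction that the SAP rules out.

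A second, separate question is what happens if more than two visits enter one linear-time fit. Person-to-person differences in slope, or correlation that decays with time, are then treated as independent residual noise.

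**Working it through.** The SAP gives no sample size, SD, correlation or dropout rate, so there is no figure of its own to reproduce. All numerical settings below are assumptions, apart from the cut of 18 and the two-sided 0.05 level.

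**1. Two visits, complete pairs.** In one simulated data set (80 per arm, cut at 18, Visit 1 and Visit 5 SDs 2.45 and 2.63), the random-intercept model and a pooled-variance comparison of change scores agree: estimate 0.2352 both ways, SE 0.4056 both ways. The residual variance is learned from within-person change, so unequal visit variances do not matter.

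**2. What the cut does to the variances.** Assume DSMQ mean 14 and SD 3 before the cut.
- Standardized cut: (18 - 14)/3 = 1.333. Normal density 0.164, cumulative probability 0.909, ratio 0.180.
- Visit 1 variance factor: 1 - 1.333 × 0.180 - 0.180² = 0.727. Variance 9 × 0.727 = 6.54, SD about 2.56.
- Visit 5 variance, test-retest ρ: 9 × (1 - ρ² × 0.273), which is 8.39 for ρ = 0.5 and 7.80 for ρ = 0.7.

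**3. The regression that the model uses.** Selection on Visit 1 leaves the true slope of Visit 5 on Visit 1 at ρ. Compound symmetry replaces it by covariance divided by a common variance. For complete data:
- ρ = 0.5: (0.5 × 6.54)/((6.54 + 8.39)/2) = 3.27/7.46 = 0.44.
- ρ = 0.7: (0.7 × 6.54)/((6.54 + 7.80)/2) = 4.58/7.17 = 0.64.

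Fitting the model in large samples with 10% random dropout in one arm and 30% baseline-dependent dropout in the other gives 0.42-0.43 and 0.63.

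**4. The resulting bias.** In an arm where completers' mean baseline exceeds that of all randomized by d, the estimated Visit 5 mean is off by (true slope - implied slope) × d. Random dropout has d = 0 and adds nothing. If low scorers leave one arm, take d = 0.7 to 1.0 points:
- ρ = 0.5: (0.50 - 0.43) × 0.7 = 0.049 to (0.50 - 0.42) × 1.0 = 0.080 points.
- ρ = 0.7: (0.70 - 0.63) × 0.7 = 0.049 to 0.07 × 1.0 = 0.070 points.
- Divided by the SD of 3: 0.016 to 0.027 SD.

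The large-sample fits give about 0.015-0.03 SD, in favor of the arm with more dropout. Truncation that excludes 25-50% of candidates gives up to 0.15-0.21 points, or 0.05-0.07 of the pre-cut SD. If high scorers leave instead, d is negative and the sign reverses. If dropout is alike in both arms, the errors cancel.

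**5. Standard error, two visits.** Simulation under no effect: 80 per arm, 1,500 runs, intraclass correlation 0.3 or 0.6.

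| Setting | Model SE / true SE | Type I error |
|---|---|---|
| Cut 18, complete | 1.00 | 0.048-0.053 |
| Cut 18, 30% random dropout | 0.99 | 0.049-0.059 |
| Cut 14 (half excluded), 30% random dropout | 0.94-0.96 | about 0.065 |

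The Monte Carlo error of a 5% rate is √(0.05 × 0.95/1500) = 0.0056, so the first two rows cannot be told apart from 5%.

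**6. More than two visits.** For balanced data with J visits, true over claimed variance of b3 is (σe² + σs² Sxx)/(σe² + σs² Sxx/(J - 1)). Assume intercept variance 0.6, σe² = 0.4 and visits at months 0, 2, 8, 14. Sxx is 34.67 for the first three and 120 for all four. With an SD of true change over 8 months of 0.5 baseline SD, σs² = (0.5/8)² = 0.0039:
- Visits 1, 3, 5: (0.4 + 0.135)/(0.4 + 0.068) = 1.145, size 6.7%.
- Visits 1, 3, 5, 6: (0.4 + 0.469)/(0.4 + 0.156) = 1.562, size 11.7%.

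For SDs of change from 0.3 to 1.0, size runs 5.7-9.8% with three visits and 7.9-18.8% with four. For J = 2 the ratio is 1.

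**7. Is the cut responsible for that?** In four-visit simulations with varying slopes, the SE ratio is 0.81 without the cut and 0.82 with it. With decaying correlation it is 0.70 and 0.73. With the cut alone it is 0.99-1.00 (type I error 0.046-0.055). The cut plays no part.

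**The case against.** The strongest defense is that the better-supported reading is a two-visit model, where the test is exact with complete pairs and the SE error at the stated cut is within simulation noise. The large type I errors need a three- or four-visit linear fit, which the text makes less likely, and slope variances that the SAP does not give. The dropout bias also needs assumed values: dropout that depends on baseline and differs between arms. All of this stands, and it limits the point to a small one.

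It does not remove the point. The SAP states without condition that differential dropout cannot bias the estimate toward the arm that loses more. Under the two-visit reading, the entry cut and baseline-dependent dropout, which is MAR, can produce a bias in exactly that direction.

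A reader might infer something stronger: that the DSMQ cut makes the error bars on b3 too small and so invalidates the primary test. The documents do not support this. The cut alone leaves the SE essentially right with two visits and with four; a severe cut in a four-visit fit gives SEs 2-6% too large, if anything. Nor does the cut argument carry over to the seven secondary outcomes, because it truncates DSMQ only.

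**Conclusion.** The covariance form is too restrictive for the MAR claim attached to it. For Visits 1 and 5 the consequence is small: none with complete pairs; with 30% random dropout an SE error of about 1%; with 10% random versus 30% baseline-dependent dropout a bias of about 0.015-0.03 SD. This rests on DSMQ mean 14, SD 3 and the cut of 18, with test-retest 0.5-0.7 for the bias and intraclass correlation 0.3 or 0.6 for the SE. Harsher truncation makes both larger.

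Conditionally, if Visits 3 or 6 enter the same linear-time fit, the SE of b3 is too small whenever slopes vary between persons or correlation decays. Type I error is then about 6-19% for slope SDs of 0.3-1.0 baseline SD over 8 months. That part is independent of the entry cut and, because the same equation serves them, could also reach the secondary outcomes measured at each visit. Medication adherence is explicitly measured on two occasions and is outside it.

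**What to change.** In SAP section 7:

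1. State that the primary model uses Visits 1 and 5 only, or list the visits entered.
2. Replace the random subject intercept by an unstructured within-subject covariance over those visits, indexed by nominal visit, fitted by REML with Kenward-Roger degrees of freedom.
3. Reword the MAR sentence so that validity is conditional on MAR and on that covariance, and drop the unconditional statement about groups with greater dropout.
4. If a fallback of random intercept plus random slope with visit-specific residual variances is wanted, restrict it to fits with more than two visits. With two visits it has at least four variance parameters (intercept, slope, two residuals) for three observable moments (two variances, one covariance) and is not identifiable.

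The cost is a sentence or two in the SAP and one line of code. The model estimates a few more variance parameters, and the reported SE may be slightly larger. With complete two-visit data the test is unchanged.

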- Differences between the two arms will be assessed among participants with a Clinical Dementia Rating (CDR) score of zero (i.e., excluding those with uncertain dementia [CDR = 0.5]).
- Differences between the two arms will be assessed among participants with and without at least 12 years of education.
- Differences between the two arms will be assessed by sex.

For each seven secondary outcomes, the primary analysis will like the primary analysis for the DMSQ.

For each primary and secondary outcome, a secondary analysis will include the primary covariates to reduce variation attributable to subject differences.

Analyses by CCT Performance

- Group differences between the two arms will be assessed among participants who complete at least 18 of the 24 CCT training sessions as well as the follow-up visit being examined (i.e. Visit 3, 5, or 6).
- Total time spent training (across all sessions by the participant) are data calculated by Cognifit and available to the investigators. This will be used to explore whether training time modifies group differences.
- CCT performance scores are calculated at each session by Cognifit using assessment measures that remain constant regardless of any changes for the participant. For those with at least 18 of 24 trainings sessions, a linear slope will be calculated to explore whether this modifies group differences.

5. Endpoints and Covariates

Endpoints

The primary endpoint is the change from baseline DSMQ to Visit 5.

Seven secondary endpoints, also change from baseline to Visit 5 (except for medication adherence), are:

- Memory – averaged from neuropsychological tests standardized using baseline scores:

Logical Memory - Immediate Recall

Logical Memory - Delayed Recall

CERAD Word List Memory – Immediate Recall

CERAD Word List Memory – Delayed Recall

CERAD Word List Memory –Recognition

- Executive function/attention – averaged from neuropsychological tests standardized using baseline scores:
 - Cancellation Test - Letter
 - Cancellation Test – Shape
 - Trail Making Test – A
 - Trail Making Test – B
 - Digit Span - Forward
 - Digit Span - Backward
- Prospective memory
 - Rivermead time-based subtest (Appointment)
- Medication adherence – by change in renewals and refills of diabetes medications between one year before Visit 1 and one year after Visit 3
- Hemoglobin A1c (HbA1c)
- Diastolic blood pressure – measured twice while sitting and at rest with a five minute interval

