- Systolic blood pressure – measured twice while sitting and at rest with a five minute interval

Primary covariates

- age
- sex
- years of education
- baseline MMSE

Secondary covariates

- site – Bronx, NY VAMC versus Ann Arbor, MI VAMC
- ethnicity – Non-Hispanic European Ancestry vs. Other
- Cognitive Self-Report Questionnaire
- Geriatric Depression Scale
- Short – Test of Functional Health Literacy in Adults
- Total Training Sessions

Calculating time

Dates of Visits 1 through 6 are recorded and individual CCT training dates are maintained by the Cognifit and available for use. As indicated in Figure 1 (above), pre-specified intervals are targeted for each visit, but actual visits vary due to scheduling

contingencies with participants and staff. Thus, intervals between assessments are determined from days since Visit 1 (baseline assessment).

6. Handling of Missing Values and Other Data Conventions

Missing data will be accounted for using iterative full information maximum likelihood estimation of the relevant model parameters.

A separate three-step procedure will be used for the sixteen neuropsychological test scores at each visit. The first two steps substitute values for missing data and the third step creates derived scores for use in analyses.

The first step is limiting the participants for whom their neuropsychological data at that visit will be analyzed. Although most participants have data on all the variables, others have some missing data. A participant's data for a visit will be analyzed only if there are at most two missing variables of the 16. A participant must have data analyzed at Visit 1, but may have data analyzed after missing other visits.

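### The primary model picks covariates by a P<0.05 imbalance test and does not condition on baseline DSMQ: the test is valid but less precise than the collected data allow

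*SAP*

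**What the plan says.** The primary outcome is a change score: "The primary endpoint is the change from baseline DSMQ to Visit 5" (section 5, Endpoints). Section 7 (Statistical Procedures) fits a linear mixed model with time, group, group by time and a random subject effect. The test is on the interaction b3, "which indicates whether the change in outcome over time differs between the intervention groups". Time is measured from baseline: "intervals between assessments are determined from days since Visit 1 (baseline assessment" (section 5, Calculating time). The group coefficient b2 is therefore the arm difference at Visit 1, and the model estimates it freely.

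Section 5 lists four primary covariates: age, sex, years of education and baseline MMSE. Baseline DSMQ is in neither the primary nor the secondary list. For the primary model, if there is a significant (P<0.05) "discrepancy between the two arms of the RCT on any of the primary covariates", then "that covariate will be included in the model".

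Two further covariate analyses are planned. Section 4 says that for every primary and secondary outcome "a secondary analysis will include the primary covariates to reduce variation attributable to subject differences". Section 7 (Measures to Adjust for Multiplicity) says of a secondary covariate that is unbalanced or correlated with an outcome that "it will be used as a covariate in a secondary analysis, to reduce within-group variation". Nowhere does the SAP say whether a covariate enters as a main effect or also by time.

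Baseline DSMQ is needed for entry: "Self-management score 18 (of a possible 20) or below on the Diabetes Self-Management Questionnaire (DSMQ" (section 2). It should therefore be available, before randomisation, for every eligible randomised participant.

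**The concern.** There are three linked weaknesses.

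1. **The trigger.** A significance test of baseline imbalance between randomised arms tests a hypothesis already known to be true. It picks covariates by chance, not by how well they predict the outcome, and the content of the primary model is unknown until the data are seen.
2. **Baseline DSMQ.** Randomisation makes the expected baseline difference zero, yet the model spends information estimating it. Baseline is used only by subtraction, which is less efficient than conditioning on it whenever the correlation is below 1.
3. **Form of entry.** If covariates enter as main effects constant over time, which is the natural reading, they explain differences between subjects in level, not in change. The adjusted analyses would then nearly repeat the unadjusted one and miss the purpose that the SAP gives for them.

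Precision of the primary comparison is at stake. Type I error and bias are not. Section 7 uses the same model for all seven secondary outcomes, so the weakness extends to them.

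**Working it through.** **Inputs.** From the SAP: four primary covariates, a P<0.05 trigger, the model above, a two-sided 0.05 test, and DSMQ of 18 or below at entry. The SAP gives no sample size, power, SD, dropout rate or correlation, so there is no planned figure to reproduce. Assumed: correlation ρ between Visit 1 and Visit 5, follow-up fraction f, the share of an otherwise normal pool that the cap excludes, 1:1 allocation, and two visits (1 and 5) in the model.

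**Trigger.** For four independent covariates, P(at least one fires) = 1 − 0.95⁴ = 0.185. With all pairwise correlations at 0.4 it is 16.6%.

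**What b3 estimates.** With complete data at a common Visit 5 time, b3 (times that interval) is the arm difference in mean change. In a simulated data set of 100 with arms made to differ by 3 years of age, the mixed model gave −0.12641 (SE 0.21356), the same as the change-score comparison. Adding age as a main effect left both figures unchanged.

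**Variance with baseline conditioning, relative to the present contrast.** Let the Visit 5 SD before truncation be 1 and v₁ the baseline variance after the cap. Per participant in an arm:

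- present contrast: (1−ρ²)/f + (1−ρ)²v₁
- conditioned on baseline: (1−ρ²)/f
- ratio: (1−ρ²) / [(1−ρ²) + f(1−ρ)²v₁]

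With f = 1 and v₁ = 1 the ratio is (1+ρ)/2. For a normal baseline cut above at c, v₁ = 1 − cλ − λ², where λ = φ(c)/Φ(c). Excluding 20% gives c = 0.842, λ = 0.350, v₁ = 0.583. Excluding 50% gives v₁ = 0.363. In the cap rows ρ is the correlation before truncation.

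Example, ρ = 0.5, cap excluding 20%, f = 0.8: 0.75 / (0.75 + 0.8 × 0.25 × 0.583) = 0.75/0.8666 = 0.87.

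| Setting | ρ=0.5 | ρ=0.6 | ρ=0.7 | 80% power becomes (ρ 0.5 to 0.7) |
|---|---|---|---|---|
| Complete, no cap effect | 0.75 | 0.80 | 0.85 | 90% to 86% |
| 20% dropout | 0.79 | 0.83 | 0.88 | 88% to 85% |
| Cap excludes 20%, complete | 0.84 | 0.87 | 0.91 | 86% to 84% |
| Cap excludes 50%, complete | 0.89 | 0.92 | 0.94 | 84% to 82% |
| Cap excludes 20%, 20% dropout | 0.87 | 0.90 | 0.92 | 85% to 83% |

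Power is Φ(2.802/√ratio − 1.960), where 2.802 = 1.960 + 0.842. With 20% dropout and no cap effect, the gain equals 27%, 20% or 14% more participants (1/ratio − 1). At ρ = 0.9, complete data and no cap effect, the ratio is 0.95 and power 82%.

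**Simulation check** (40,000 trials, assumed 75 per arm, complete data). The empirical variance ratio of ANCOVA to change score was 0.755 (ρ 0.5) and 0.854 (ρ 0.7) without the cap, and 0.843 and 0.916 with the cap excluding 20%. Type I error was 0.049 to 0.052 for both methods. In separate null simulations (6,000 trials per setting, assumed N of 60 to 200), the SAP rule with main-effect entry gave 4.7% to 5.2%. It gave 4.3% to 4.9% if the selected covariate could also act on change.

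**Main-effect covariates under realistic data** (1,500 runs per setting, assumed covariate coefficient 0.4 SD). With complete data at common times, b3 and its SE changed by 0.000. With 20% dropout, with or without variation in visit times, the mean SE change was −0.3% to −0.5% and the mean shift in b3 was 0.06 to 0.10 SE (largest single run 0.53 SE).

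**The case against.** The primary test is valid and targets the stated endpoint, so this is a choice between two sound estimators. Baseline DSMQ is already in the model as the first repeated measure. The trigger is fully written down, with named covariates, a threshold and an action, and an always-adjusted secondary analysis stands beside it. On main-effect entry the trigger costs almost no precision. Every size above rests on assumed values, and the larger gains ignore either the cap or dropout. ANCOVA on the Visit 5 value would drop participants without that visit and ignore actual visit days, which sits badly with the ITT set and the full-information likelihood. Recruitment was complete when the SAP was written, so replacing the primary model needs justification.

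Much of this stands. There is no bias and no inflated error rate, and the precision loss comes from the free baseline term, not from the trigger. With the cap and dropout combined the gain is modest. None of it removes the point: the gain is positive for any ρ below 1, and the trigger still leaves the primary model to chance. A mixed model with a common baseline mean keeps every randomised participant and the actual visit days, which answers the ANCOVA objection.

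**Conclusion.** The concern holds, as an improvement to precision and not as an error in the test. The covariate rule for the primary model responds only to chance imbalance, with about a 17% to 19% probability of changing the model. Separately, the model forgoes conditioning on a baseline value that the trial already holds. For ρ of 0.5 to 0.7 the variance could fall to between 0.75 and 0.85 of its present value in the simplest case, and to about 0.87 to 0.92 when 20% dropout and a cap excluding 20% act together. A higher correlation or a more severe cap shrinks the gain further. The covariate analyses in sections 4 and 7 will add almost nothing to the treatment test if they use main effects only. The sizes depend on the assumed ρ, dropout and cap effect; the direction does not.

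**What to change.** In section 7 (Statistical Procedures):

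- Delete the P<0.05 imbalance trigger.
- Always condition on baseline DSMQ in the primary model. A mixed model with a common baseline mean (b2 dropped) and variances allowed to differ by visit fits the rest of the SAP best. The separate variances matter because the entry cap can make Visit 1 less variable than Visit 5. ANCOVA on the Visit 5 value is the simpler alternative, with its handling of missing Visit 5 data stated.
- Name in advance any further covariates in the primary model, and state that they act on change: by a covariate-by-time term, or as terms in the ANCOVA.
- State the same form of entry for the covariate analyses in section 4 and in section 7 (Measures to Adjust for Multiplicity).
- Keep the present unadjusted model as a supportive analysis.

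The cost is SAP wording and a few degrees of freedom, with no new data. Because recruitment is finished, the change should be dated and justified before outcomes are compared by arm.

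### With no covariate-by-time term written, covariate adjustment would barely affect the group-by-time test, and the covariate list includes a post-randomisation variable

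*SAP*

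**What the plan says.** Section 7 (Statistical Procedures) writes the model out in full: intercept, time, group, group by time, a term that "is the subject random effect, and" a residual. The effect of interest is the group-by-time coefficient, "which indicates whether the change in outcome over time differs between the intervention groups". The main comparison is Visit 1 with Visit 5.

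Covariates come in by three routes:

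- **Section 7, Statistical Procedures.** If the arms differ on a primary covariate (age, sex, years of education, baseline MMSE) at P < 0.05, "that covariate will be included in the model". This can change the primary model.
- **Section 4.** For every outcome, a secondary analysis "will include the primary covariates to reduce variation attributable to subject differences".
- **Section 7, Measures to Adjust for Multiplicity, Confounders, Heterogeneity, Etc.** Secondary covariates are screened: "if any are unbalanced or correlate with an outcome at" p < 0.05, then "it will be used as a covariate in a secondary analysis, to reduce within-group variation".

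None of the three says whether a covariate enters as a main effect only or also in interaction with time. The screening rule does not say whether correlation with an outcome means its level or its change.

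The secondary covariates in section 5 are site, ethnicity, three questionnaire or test scores and "Total Training Sessions".

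**The concern.** The random intercept already absorbs stable differences between participants. A baseline covariate entered as a main effect explains part of those same differences. It says nothing about who changes more, and change is what b3 measures. The adjusted analyses would then be almost the same analysis as the unadjusted one. Agreement between them would carry little information, and section 8 plans no sensitivity analysis. Any precision available from covariates that predict change would be left unused, and an arm imbalance in such a covariate would remain in b3.

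The selection rule adds two weaknesses. The covariate set is decided by p values from the trial's own data and may differ across the eight outcomes. It can also admit the number of training sessions completed, which is behaviour under the assigned programme. Adjusting for that departs from the intent-to-treat comparison of section 3.

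**Working it through.** The SAP gives no sample size, variance, correlation or dropout rate, so there is no stated figure to reproduce. The algebra needs none of these. The sizes below rest on assumed values.

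**1. Algebra, complete data, Visit 1 at t = 0 and Visit 5 at t = 1 for everyone.** Add a baseline covariate X with main effect γ and, possibly, an effect δ on change. The within-participant change is

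D = Y5 − Y1 = b1 + b3·Group + γ(X − X) + δX + (e5 − e1).

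The γ term is zero. Without an X-by-time term in the model:

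- the estimate of b3 is the difference between arms in mean D, whether or not the main effect of X is fitted;
- its expectation, given the observed arms, is b3 + δ × (difference in mean X);
- its variance is 2σe²(1/n1 + 1/n2), where σe² is the fitted residual variance. The subject variance does not appear.

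**2. Numerical check, complete data (N = 160, 80 per arm, REML).** In a run where X has δ = 0.4, the main effect reduced the subject variance from 1.362 to 0.596 and left the residual variance at 0.582. The by-time term reduced the residual variance to 0.495. The formula gives:

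- without X, or with its main effect: √(2 × 0.582 × 2/80) = 0.171 (simulated 0.170);
- with X by time: √(2 × 0.495 × 2/80) = 0.157 (simulated 0.158).

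The mean ratio of standard errors was 1.000 for the main effect and 0.926 for the by-time term.

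**3. Imbalance.** With 80 per arm, a difference in X reaches p < 0.05 at about 1.96 × √(2/80) = 0.31 SD. An imbalance of 0.4 SD is therefore one that the SAP's rule would flag. The expected shift in b3 is 0.4 × 0.4 = 0.16. Simulated means, true b3 = 0.30:

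| Setting | No covariate | Main effect | Main effect + by time |
|---|---|---|---|
| Complete data, imbalance 0.4 SD | 0.466 | 0.466 | 0.293 |
| 20% dropout, varying visit times, imbalance 0.4 SD | 0.475 | 0.473 | 0.292 |

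**4. Dropout and varying visit dates.** Section 2 expects attrition, section 5 uses actual days since Visit 1, and section 6 uses full-information likelihood, so exact cancellation fails. Assumed ranges: correlation of X with the outcome 0.2 to 0.5, intraclass correlation 0.5 to 0.7, visit-time spread 10%. For a main effect only:

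| Setting | Mean shift in b3, in SE | Mean SE ratio |
|---|---|---|
| Complete data | 0.01 to 0.03 | at least 0.999 |
| 10 to 30% dropout | 0.02 to 0.14 | 0.985 to 0.9996 |

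The largest shift in any single simulated dataset was 0.50 SE. A separate simulation with 120 participants and 20% dropout gave ratios of 0.97 to 0.99 for the SD of b3. Across both, the reduction runs from almost nothing to about 3%.

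**5. What the by-time term can gain.** In the 120-participant simulation with complete data, the ratio was 0.985, 0.97 and 0.91 when covariates explained 5%, 10% and 20% of the variance of change. If X does not predict change there is no gain: about 1.00 to 1.02 with complete data.

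**6. How often the primary-model rule fires.** Treating the four primary covariates as independent, the chance that at least one is imbalanced at P < 0.05 is 1 − 0.95⁴ = 0.185.

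**The case against.** The strongest reply is that the SAP never says covariates enter as main effects only. That is correct. The main-effect reading is an inference from a model written term by term with no covariate-by-time term, and from wording that speaks only of including a covariate. If by-time terms were intended, the SAP needs to say so, and the remedy is the same.

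Second, the SAP's stated aim concerns variation between subjects or within groups; it does not promise a smaller standard error for b3. A main effect does reduce the subject variance, so the statement is not false. What fails is any benefit to the test that the trial relies on.

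Third, baseline covariates can make the missing-at-random assumption more plausible, and with dropout b3 does move somewhat. This stands, and it is why the effect is described as nearly inert and not as nil.

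Fourth, if main effects are nearly inert, then Total Training Sessions as a main effect does little harm. This also stands in part. The variable becomes harmful once covariates enter by time, so it has to go when that change is made.

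A reader might further infer that the p < 0.05 screen inflates the type I error. The simulation does not support this: rejection rates under the null were 4.2% to 5.5% with 60 per arm and five covariates. Nor does the SAP say that adjusted results will be presented as confirming the unadjusted ones; that is only a risk of interpretation.

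**Conclusion.** The point holds in a limited form. Under the model as written, with covariates read as main effects, adjustment leaves b3 and its standard error exactly unchanged for complete data at common visit times. It lowers the standard error by about 3% at most under the assumed dropout. It does not correct imbalance in a covariate that predicts change. The post-randomisation variable on the list is a separate defect, and it is plain from the text.

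It would go too far to say that the estimate is always unchanged, or that the primary analysis is invalid. The secondary-covariate screen touches secondary analyses only. The primary-covariate rule can touch the primary model but would seldom move its result much. The precision forgone depends on how well the covariates predict change, which the SAP gives no means of judging: the assumed cases range from no gain to a standard error about 9% smaller. This is a change worth making, not a threat to the validity of the trial.

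**What to change.** - Replace both p < 0.05 screens with one pre-specified set of baseline covariates, the same for all eight outcomes, drawn from the listed primary covariates and the baseline secondary covariates.
- State the form of entry. Either give each covariate a main effect and a covariate-by-time term in the existing mixed model, or use the covariates in a Visit 5 model adjusted for the baseline value of the outcome. The first keeps participants without Visit 5 in the likelihood; the second, in its simplest form, does not.
- Remove Total Training Sessions from the adjustment covariates and keep it for the exploratory analyses by CCT performance in section 4.
- Close the list. Section 7 gives computer experience as an example and section 6 calls the performance slope a secondary covariate, yet neither is listed in section 5. The slope is also measured after randomisation and belongs with the exploratory analyses.

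The cost is SAP wording, a few extra model terms and a few degrees of freedom. If the chosen covariates do not predict change, the gain is nil and the standard error may rise by 1 to 2%.
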